5.5.2. Other Comparisons of Interest

If the primary comparison of interest (Section 5.5.1) using the ITT-E population demonstrates non-inferiority of Q8W compared to Q4W then the following key secondary comparisons will be tested:

- Treatment with Q8W will be declared non-inferior to Q4W with respect to the proportion of participants with HIV-1 RNA < 50 c/mL at Week 48 (defined by the US FDA snapshot algorithm) if the lower end of a two-sided 95% confidence interval for the difference between in rates (Q8W – Q4W) lies above -10% using the ITT-E population

- Superiority of Q8W compared to Q4W with respect to change from baseline HIVTSQs total score at Week 48 using the ITT-E population and a two-sided 5% level of significance. Refer to Section 12.5.1 for details.

For the primary endpoint treatment comparison at Week 48, no multiple comparison adjustment is necessary for testing non-inferiority followed by superiority (conditional on achieving a significant test for non-inferiority) since testing follows a pre-specified sequence of hypothesis such that if the first hypothesis tested is not significant, all subsequent tests will not be performed. This fixed sequence procedure controls the type I error rate at the nominal level. The primary endpoint treatment comparison at Week 48 will also be performed using the PP population and the results will be compared for consistency with the results from the ITT-E population.

In addition to the primary and the key secondary comparisons, the comparisons between two treatment arms for ACCEPT (general acceptance score), PIN (Domain scores (Bother of ISRs, Leg movement, Sleep, and Acceptance) and Individual Items Scores (Anxiety before, Pain, Satisfaction, Anxiety After, Willingness)), HAT-QoL (Life satisfaction, HIV medications, disclosure worries) and HIVTSQc (Treatment Satisfaction score) at timepoints through Week 48 will also be performed as supportive analyses.

Lastly, for the IDMC interim analyses, since the statistical stopping guidelines will not result in early stopping for positive efficacy findings, these interim treatment comparisons will not inflate the Type I error rate for the primary treatment comparison.

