| 
 The analysis for HIVTSQs, ACCEPT and HAT-QoL will be performed for subjects with and without prior exposure to CAB+RPV separately. 
 For subjects without prior exposure to CAB+RPV, an analysis of covariance (ANCOVA) model will be used at each visit during the maintenance phase with covariates: treatment, age (<50, ≥ 50 years old), sex at birth, race (i.e. white, non-white) and baseline score value for other endpoints (as a continuous variable). For subjects with prior exposure to CAB+RPV, an analysis of covariance (ANCOVA) model will be used at each visit during the maintenance phase with covariates: treatment, age (<50, ≥ 50 years old), prior exposure to CAB+RPV (i.e. 1 to 24 weeks, >24 weeks), sex at birth, race (i.e. white, non-white) and baseline score value (as a continuous variable). For PIN, an analysis of covariance (ANCOVA) model will be used at each visit during the maintenance phase with covariates: treatment, age (<50, ≥ 50 years old), prior exposure to CAB+RPV (i.e. 0 weeks, 1 to 24 weeks, >24 weeks), sex at birth, race (i.e. white, non-white), and Week 8 score value (as a continuous variable). Adjusted point estimates will be derived as LSMEANS using the observed margins (OM) option within PROC MIXED in SAS. The superiority testing of Q8W compared to Q4W with respect to change from baseline in HIVTSQs total score at Week 48 will be performed using the fixed sequence procedure to control for the type I error rate at the nominal level of 5%. If the superiority testing within subjects without prior exposure to CAB+RPV demonstrates Q8W is superior to Q4W in change from baseline in HIVTSQs total score at Week 48 at two-sided 5% level of significance, the superiority testing at the same level of significance (i.e. two-sided 5%) within subjects with prior exposure to CAB+RPV will be followed. No adjustment for multiplicity will be applied for other tests as they will be considered supportive. Interactions between treatment and each of the covariates will not be assessed unless the exploratory subgroup analyses on the primary endpoint highlights significant interactions. In this situation, the interaction(s) of interest will be assessed and, if necessary, results will be reported in the clinical study report. Interactions between treatment and the baseline score will be investigated but not included in the model. If interactions are found to be significant ($p < 0.10$), results may be presented separately by subgroup. | |

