| 6.21 | NA | NA | Intent-to-Treat Exposed | 201585/primary_02/T7.24 | Statistical Analysis of HIVTSQs - Change from Baseline in Total Treatment Satisfaction Score by Visit for Subjects without Prior Exposure to CAB+RPV - LOCF (Maintenance Phase) | Adjust column header and footnote as appropriate. | W48 |
| 6.22 | NA | NA | Intent-to-Treat Exposed | 201585/primary_02/T7.24 | Statistical Analysis of HIVTSQs - Change from Baseline in Total Treatment Satisfaction Score by Visit for Subjects with Prior Exposure to CAB+RPV - LOCF (Maintenance Phase) | Adjust column header and footnote as appropriate. | W48 |

CONFIDENTIAL

207966

| Health Outcomes Tables | | | | | | | |
|--|------------|------------|------------|-------------------------|--|---|-------------|
| No. in W48 | No. in W96 | No. in EOS | Population | IDSL / Example Shell | Title | Programming Notes | Deliverable |
| HIV Treatment Satisfaction Questionnaire Change Version (HIVTSQc) | | | | | | | |
| 6.23 | NA | NA | Q4W ATLAS | 201584/primary_01/T6.25 | Proportion of Subjects with HIVTSQc - Individual Item Change Score at Week 48 (Maintenance Phase) for Subjects from Q4W ATLAS | | W48 |
| 6.24 | NA | NA | SOC | 201584/primary_01/T6.25 | Proportion of Subjects with HIVTSQc - Individual Item Change Score at Week 48 (Maintenance Phase) for Subjects from SOC | | W48 |
| 6.25 | NA | NA | Q4W ATLAS | 201584/primary_01/T6.26 | Summary of HIVTSQc – Total Treatment Satisfaction Change Score at Week 48 (Maintenance Phase) for Subjects from Q4W ATLAS | | W48 |
| 6.26 | NA | NA | SOC | 201584/primary_01/T6.26 | Summary of HIVTSQc – Total Treatment Satisfaction Change Score at Week 48 (Maintenance Phase) for Subjects from SOC | | W48 |
| 6.27 | NA | NA | Q4W ATLAS | 201584/primary_02/T6.41 | Summary of HIVTSQc – Individual Item Change Score at Week 48 (Maintenance Phase) for Subjects from Q4W ATLAS | | W48 |
| 6.28 | NA | NA | SOC | 201584/primary_02/T6.41 | Summary of HIVTSQc – Individual Item Change Score at Week 48 (Maintenance Phase) for Subjects from SOC | | W48 |
| 6.29 | NA | NA | Q4W ATLAS | 201584/primary_01/T6.27 | Statistical Analysis of HIVTSQc – Total Treatment Satisfaction Change Score at Week 48 (Maintenance Phase) for Subjects from Q4W ATLAS | Adjust column header and footnote as appropriate. | W48 |

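### Section 5.5.2 states one HIVTSQs superiority hypothesis for ITT-E, but Section 12.5.1 tests two ordered prior-exposure strata and never tests ITT-E

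*SAP*

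**What the plan says.** SAP Section 5.5.2 lists, among the key secondary comparisons tested once primary non-inferiority is shown, "Superiority of Q8W compared to Q4W with respect to change from baseline HIVTSQs total score at Week 48 using the ITT-E population". The test level is 5%, two-sided, and the item leaves the method to Section 12.5.1. This is one hypothesis, one population and one level.

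Section 12.5.1 sets the method differently. "The analysis for HIVTSQs, ACCEPT and HAT-QoL will be performed for subjects with and without prior exposure to CAB+RPV separately". It invokes a "fixed sequence procedure to control for the type I error rate at the nominal level of 5" per cent and gives the order: "If the superiority testing within subjects without prior exposure to CAB+RPV demonstrates Q8W is superior to Q4W" at Week 48, then "the superiority testing at the same level of significance (i.e. two-sided 5%) within subjects with prior exposure to CAB+RPV will be followed".

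The displays in Section 15.15.5.10 follow 12.5.1. Table 6.21 is the model for "Change from Baseline in Total Treatment Satisfaction Score by Visit for Subjects without Prior Exposure to CAB+RPV", and Table 6.22 is its counterpart for participants with prior exposure. Both carry the ITT-E label. Section 12.2 defines the main-study summary measure as the Q8W minus Q4W mean difference, with no mention of a split.

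In the ANCOVA for participants without prior exposure, the last covariate reads "baseline score value for other endpoints (as a continuous variable"). The parallel model for participants with prior exposure lists the baseline score without that qualifier.

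**The concern.** A multiplicity section has to name the hypothesis that carries the alpha. Here it names an ITT-E hypothesis, while the methods section spends the alpha on two stratum hypotheses. Neither section says what may be claimed if the first test succeeds and the second fails. In that case the evidence concerns only participants who entered without prior CAB+RPV exposure, whereas 5.5.2 read on its own suggests a conclusion for the whole randomised and exposed population.

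The covariate wording adds a smaller ambiguity to the first test in the sequence. The phrase about other endpoints has no counterpart in the sentence, so a literal reader cannot tell whether the HIVTSQs model adjusts for the baseline HIVTSQs score.

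**Working it through.** **1. Is there an ITT-E test of change from baseline anywhere in the SAP?**
- Section 12.5.1: HIVTSQs is modelled only within each exposure group.
- Section 15.15.5.10: Tables 6.21 and 6.22 are the two stratum models. Tables 6.18 to 6.20 (descriptive change from baseline) are also split by exposure. Tables 6.16 and 6.17 pool the strata, but they summarise scores by visit and contain no comparison.
- By contrast, the PIN model in Section 12.5.1 is a single ANCOVA with prior exposure (0, 1–24, >24 weeks) as a covariate, so the SAP already contains a pooled template.

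The ITT-E difference in change from baseline is therefore neither modelled nor tested.

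**2. Does the sequence hold its stated 5%?** Let H1 be no difference without prior exposure and H2 no difference with prior exposure.
- If H1 is true, any false rejection requires rejecting H1, which has probability at most 5%.
- If H1 is false and H2 is true, the only false rejection is of H2, again at most 5%.

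A simulation with independent strata (4 million draws, both nulls true) gave 5.0%. Testing both strata without an order would give 1 − 0.95² = 9.75%. The SAP's figure is reproduced.

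**3. What does each outcome support?**
- Step one fails: no superiority claim.
- Step one succeeds, step two fails: a claim for participants without prior exposure only.
- Both succeed: a claim in each stratum, which together make up ITT-E.

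**4. How would power compare with a pooled test?** Inputs: 1020 randomised 1:1 (Section 2.3), so 510 per arm. The share f without prior exposure is not in the SAP and is varied. Standardised effects are assumed.

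Power with n per arm and standardised effect d: Φ(d·√(n/2) − 1.96).

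For 80% pooled power, d = (1.960 + 0.842)·√(2/510) = 0.175. For 90%, d = 0.203. With the same effect in both strata, step one uses n = 510f, and both steps succeed with probability equal to the product of the two stratum powers:

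| f | Step one (pooled 80%) | Both steps | Step one (pooled 90%) | Both steps |
|---|---|---|---|---|
| 0.3 | 34% | 22% | 43% | 33% |
| 0.5 | 51% | 26% | 63% | 40% |
| 0.6 | 58% | 25% | 71% | 38% |
| 0.8 | 71% | 17% | 83% | 25% |

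With unequal effects, the pooled effect is f·d0 + (1 − f)·d1, where d0 is the effect without and d1 the effect with prior exposure:
- d0 = 0.2, d1 = 0, f = 0.6: pooled effect 0.12, pooled power 48%, step one 70%.
- d0 = 0, d1 = 0.2, f = 0.4: pooled effect 0.12, pooled power 48%, step one 2.5% in favour of Q8W.

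The comparison can go either way.

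**The case against.** Section 5.5.2 sends the reader to 12.5.1, where the strata and their order are explicit, and the titles of Tables 6.21 and 6.22 name the stratum. ITT-E can be read as an analysis-set label (analysed as randomised) rather than a statement of the hypothesis. Separate models also have a rationale: baseline satisfaction refers to oral standard of care for one group and to 4-weekly injections for the other, so change from baseline does not mean the same thing in both. As for the covariate, the endpoints modelled there are changes from baseline and the section requires the treatment-by-baseline interaction to be examined, so the baseline score is very probably intended.

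Most of this stands, and it argues against replacing the stratum tests. It does not remove the mismatch: the cross-reference leads to different hypotheses, and no rule limits the claim after step one.

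A reader might infer three stronger points that the documents do not support:
- **That only participants without prior exposure are tested.** The prior-exposure stratum follows at the same level once the first test succeeds.
- **That type I error is inflated.** Suppose the ITT-E average were zero with +0.2 SD in the unexposed. Step one would favour Q8W in 62–76% of trials for unexposed shares of 50–70%. That is ordinary power for a true stratum effect. It misleads only if reported as an ITT-E result, and the scenario needs an opposite effect of −0.2 to −0.47 SD in the other stratum.
- **That power is necessarily lost.** The SAP states no HIVTSQs effect, SD, power or stratum split, and the direction reverses when the effect lies mainly in the unexposed.

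**Conclusion.** The concern holds as an inconsistency that changes what may be concluded. The ITT-E hypothesis stated in 5.5.2 is not tested. The tested hypotheses are two ordered stratum comparisons, and success at the first alone supports a claim only for participants without prior exposure. This conclusion rests on the text and needs no assumption.

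Alpha within the HIVTSQs sequence is controlled at 5%. The power figures are illustrations: they assume 510 per arm, a normal approximation and chosen stratum shares and effects, so no fixed loss can be attributed to the plan. The covariate wording is a drafting fault with an evident intended meaning, but it sits in the first alpha-controlled HIVTSQs model and should be corrected. The matter concerns a key secondary claim and leaves the primary endpoint untouched.

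**What to change.** 1. Restate the HIVTSQs item in 5.5.2 as the two ordered hypotheses of 12.5.1: without prior exposure first, then with prior exposure, each at two-sided 5%.
2. Add that a superiority claim is limited to participants without prior exposure unless the second test also succeeds.
3. In the no-prior-exposure ANCOVA, remove the words about other endpoints, so that the baseline score of the endpoint analysed (here HIVTSQs) is plainly a covariate, as in the parallel model.
4. Add one ITT-E ANCOVA of Week 48 change in HIVTSQs total score, with treatment, prior exposure (0, 1–24, >24 weeks), baseline score, age, sex and race, labelled supportive.

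The pooled model should not replace the confirmatory sequence. Section 5.4.2 refers to data that arrived after the Week 48 data cut and Section 15.6.7 to a source accessed in March 2022, so this version postdates that cut and a new alpha-controlled test would be post hoc. The pooled estimate would also average over two entry groups with different baseline treatments, so the stratum results should stay beside it.

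The cost is SAP wording and one extra model and display on data already collected.

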5.6. Other Considerations for Data Analyses and Data Handling Conventions

Other considerations for data analyses and data handling conventions are outlined in the appendices:

| Section | Component |
|---------|--|
| 15.2.3 | Error! Not a valid result for table. : Assessment Windows |
| 15.4 | Appendix 4 : Study Phases and Treatment State |
| 15.5 | Appendix 5 : Data Display Standards & Handling Conventions |
| 15.6 | Appendix 6 : Derived and Transformed Data |
| 15.7 | Appendix 7 : Reporting Standards for Missing Data |
| 15.8 | Appendix 8 : Values of Potential Clinical Importance |
| 15.9 | Appendix 9 : Snapshot Algorithm Details |
| 15.10 | Appendix 10 : Variables Defined for Time to Event Analysis |
| 15.11 | Appendix 11 : Identification of Adverse Events of Special Interest |
| 15.12 | Appendix 12 : Identification of COVID-19 Adverse Events |
| 15.13 | Appendix 13 : IDMC |

6. STUDY POPULATION ANALYSES

6.1. Overview of Planned Study Population Analyses

The study population analyses will be based on the Intent-to-Treat Exposed population, unless otherwise specified.

Study population analyses including analyses of subject's disposition, protocol deviations, demographic and baseline characteristics, prior and concomitant medications, and oral study treatment accountability will be based on GSK Core Data Standards.

[Table 1](#) provides an overview of the planned study population analyses, with details of the planned displays are presented in [Appendix 15: List of Data Displays](#).

Table 1 Overview of Planned Study Population Analyses

| Display Type | Data Displays Generated | |
|--|-------------------------|------------------|
| | Table | Listing |
| Randomization | | |
| Randomization ^[1] | | Y ^[2] |
| Subject Disposition | | |
| Study Populations ^[3] | Y | |
| Study Recruitment ^[3] | Y | |
| Reasons for Screening Failures ^[3] | Y | Y |
| Rescreened Subjects ^[3] | | Y |
| Age Ranges | Y | |
| Subject Disposition | Y ^{[4][5]} | |
| Reasons for Withdrawal | Y ^{[4][5]} | Y |
| IP Discontinuation | Y | Y |
| Important Protocol Deviations | Y | Y |
| Deviations leading to exclusion from PP | Y | Y |
| Inclusion and Exclusion Criteria Deviations | Y | Y |
| Demography and Baseline | | |
| Demographics Characteristics ^[6] | Y | Y |
| Race & Racial Combinations ^[7] | Y | Y |
| Hepatitis Status at Entry | Y | |
| Baseline CDC Classification of HIV infection (2014) | Y | |
| Baseline Cardiovascular Risk Assessments | Y | |
| Distribution of CD4+ Cell Counts at Screening and Baseline | Y | |
| Prior Exposure to CAB+RPV | Y | |
| HIV-1 Risk Factors | Y | |

| Display Type | Data Displays Generated | |
|---|-------------------------|---------|
| | Table | Listing |
| Medical Conditions, Concomitant Medications & Antiretroviral Therapy | | |
| Medical Conditions (Current/Past) ^[8] | Y | |
| Medical Conditions: Sub-conditions (Current/Past) ^[9, 10] | Y | |
| Concomitant Medications (non-ART) | Y ^[10] | |
| Prior ART Medications | Y | Y |
| Concomitant ART Medications during Maintenance Phase | | Y |
| ART Medications Received during LTFU Phase | | Y |
| Lipid Modifying Agents (Baseline and during Maintenance Phase) | Y | |
| Substance use at Entry | Y | |
| Medical History of Seizure | | Y |
| Other | | |
| Oral Study Treatment Accountability ^[11] | | Y |
| Transition to CAB+RPV LA Marketed Product | | Y |

NOTES:

- T = Tables, L = Listings, Y = Display Generated,
- 1. Base on Randomized population.
- 2. One listing of participants randomized but not treated, and one listing of randomized and actual strata and treatment assignment.
- 3. All Subjects screened population.
- 4. Participants who have not been recorded as either completing or withdrawing from the study will be categorized as "Ongoing at time of the analysis" for summary purposes.
- 5. Analysis of subject disposition will be performed for each Study Phase separately, as well as for overall study conclusion.
- 6. Age and ethnicity collected at Screening; weight and height collected at Baseline.
- 7. The five high level FDA race categories and designated Asian subcategories will be summarised along with all combinations of high level categories which exist in the data. The nine race categories collected will be summarised along with categories for mixed race. A by-subject listing of race will also be produced.
- 8. Medical conditions will be coded using the Medical Dictionary for Regulatory Activities (MedDRA).
- 9. Sub conditions are Cardiac, Gastrointestinal, Metabolism and Nutrition, Psychiatric, Renal and Urinary, and Nervous System Conditions.
- 10. summarised by, Ingredient combinations.
- 11. Dispensation information (dates and number of tablets dispensed and returned).

6.2. Prior and Concomitant Medications

Non-ART and/or ART Medications will be classified by categories shown in [Table 2](#). The same medication may be classified by more than one category. For example, if the medication was started after the maintenance treatment start date and was stopped at nominal Week 104 visit while subject was still receiving study treatment, this medication would be considered both 'concomitant during maintenance' and 'concomitant during extension'.

Table 2 **Derived Data for Non-ART Medications/ART Medications**

| | Definition |
|--|---|
| Prior | Medication Taken < Maintenance Treatment Start Date |
| Concomitant during Maintenance | 
For subjects continuing into Extension Phase: Maintenance Treatment Start Date^[a] ≤ Medication Taken < Date of Nominal Week 100 Visit
 
For subjects not continuing into Extension Phase: For participants continuing into LTFU Phase: Maintenance Treatment Start Date^[a] ≤ Medication Taken < LTFU ART Start Date^[b]
 |
| Concomitant during Extension | 
For subjects continuing into Extension Phase and not entering the sub-study: If subjects continued into LTFU Phase after the Extension phase: Date of Nominal Week 100 Visit^[c] ≤ Medication Taken < LTFU ART Start Date If subjects transitioned to marketed product/alternative HAART and did not withdraw study due to safety related reason, then Date of Nominal Week 100 Visit^[c] ≤ Medication Taken < Date of end of study +35 days (Q4W) or + 63 days (Q8W)
 
For subjects continuing into Extension Phase, entering the sub-study but not returning to Extension Phase: Date of Nominal Week 100 Visit^[c] ≤ Medication Taken < Date of First Sub-study Record
 
For subjects continuing into Extension Phase, entering the sub-study and returning to Extension Phase: Before the sub-study: Date of Nominal Week 100 Visit^[c] ≤ Medication Taken < Date of First Sub-study Record After the sub-study:
 
For participants continuing into LTFU Phase after return to extension phase: End of Sub-study Date^[c] < Medication Taken < LTFU ART Start Date^[b]
 
For participants transitioned to marketed product/alternative HAART and did not withdraw study due to safety related reason: End of Sub-study Date^[c] < Medication Taken < Date of end of study +35 days (Q4W) or + 63 days (Q8W)
 |
| Concomitant during Sub-study Screening | 
For subjects entering the sub-study and not receiving any thigh injection: If participants continued into LTFU Phase after the sub-study, then Date of First sub-study record ≤ Medication Taken < LTFU ART Start Date^[b] If participants transitioned to marketed product/alternative HAART and did not withdraw study due to safety related reason, then Date of First sub-study record ≤ Medication Taken < Date of end of study +35 days (Q4W) or + 63 days (Q8W)
 
If participants continued into Extension Phase after the sub-study, then Date of First sub-study record ≤ Medication Taken ≤ End of Sub-study Date^[c]
 
For participants entering the sub-study and receiving thigh injection(s): Date of First sub-study record ≤ Medication Taken < Date of First Thigh Injection
 |

| | |
|--|--|
| Concomitant during Thigh Injection | 
For participants continuing into Return to Gluteal Injection Phase: Date of First Thigh Injection^[a] ≤ Medication Taken < Date of Nominal Sub-study Week 16 Visit^[c]
 
For participants not continuing into Return to Gluteal Injection Phase: If participants continued into LTFU Phase after the sub-study, then Date of First Thigh Injection ≤ Medication Taken < LTFU ART Start Date^[b] If participants continued into Extension Phase after the sub-study, then Date of First Thigh Injection ≤ Medication Taken ≤ End of Sub-study Date^[c] If participants transitioned to marketed product/alternative HAART and did not withdraw study due to safety related reason, then Date of First Thigh Injection ≤ Medication Taken ≤ Date of end of study +35 days (Q4W) or + 63 days (Q8W)
 |
| Concomitant during Return to Gluteal Injection | 
For participants continuing into Extension Phase after the sub-study: Date of Nominal Sub-study Week 16 Visit^[c] ≤ Medication Taken ≤ End of Sub-study Date^[c]
 
For participants continuing into LTFU Phase after the sub-study: Date of Nominal Sub-study Week 16 Visit^[c] ≤ Medication Taken < LTFU ART Start Date^[b]
 
For participants transitioned to marketed product/alternative HAART and did not withdraw study due to safety related reason: Date of Nominal Sub-study Week 16 Visit^[c] ≤ Medication Taken ≤ Date of end of study +35 days (Q4W) or + 63 days (Q8W)
 |
| Received during Long-term Follow-up | 
For subjects Who received at least one CAB and/or RPV injection and have started LTFU ART: Medication Taken ≥ LTFU ART Start Date
 |

NOTES:

- Please refer to [Appendix 7](#): Reporting Standards for Missing Data for handling of missing and partial dates for medications. Use the rules in this table if medication date is completely missing.
- [a] The ART medication stopped on start date of Maintenance treatment will be considered a prior medication and will not be considered concomitant during the Maintenance phase. If the stop date of ART medication is completely missing and this medication is recorded in eCRF as prior (e.g. prior ART or prior ATLAS ART forms), it will be considered a prior medication and will not be considered concomitant during the Maintenance phase.
- [b] If subjects have missing LFTU ART start date, only the lower bound will be considered in the derivation.
- [c] Refer to Section [15.6.1](#) for the definition.

